**STATISTICS**

To the case series will be applied a descriptive statistic.

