## BACKGROUND

Ewing sarcoma, commonly bearing a pathognomonic *EWS-FL1* translocation, is the second most common bone malignancy in children and adolescents, with an annual incidence of 200–500 cases in the United States and of 120-150 cases in Italy [1,2]. With advances in multidisciplinary care, 5-year survival rates for pediatric Ewing sarcoma patients have improved from 50% during the period from 1983–1990 to 70% during the period from 2004–2016 [1-3]. Prolonged disease-free survival is achieved in the majority of patients with localized Ewing sarcoma after treatment with multiagent chemotherapy and primary tumor control [3]. The best predictive factor is histologically determined chemotherapy-induced necrosis assessed in resected primary tumors, that has allowed to identify patients who are candidates for more intensive or novel therapies [3-6]. The good and poor responder patients to neo-adjuvant chemotherapy has been defined to different systems published in literature: true Percentage, Huvos System and Bologna System [4-7].

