## OBJECTIVE OF THE STUDY

The aim of the present study is to evaluate which is the best scoring tool to determine the histological response to chemotherapy in localized Ewing sarcoma of bone.

The study will exam all the different systems to evaluate the histological necrosis after neo-adjuvant chemotherapy in all patients with localized Ewing sarcomas of bone surgically treated between 1982 and 2012.

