## STUDY DESIGN

This is single institution cases series review of histological and clinical data

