**MATERIAL AND METHODS**

We will retrieve from the database of the Rizzoli institute all the cases with a histological diagnosis of Ewing sarcoma from 01 Jan 1982 to 31 Dic 2012.

We expect to find approximately 500 cases.

We will review all the medical records, and histological data of these cases.

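### The only aim is to find the best scoring system, but the plan fixes a descriptive analysis and gives no criterion for best

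*Protocol*

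**What the plan says.** **Aim (Protocol, Objective of the Study).** One aim is given: to "evaluate which is the best scoring tool to determine the histological response to chemotherapy" in localized Ewing sarcoma of bone. The next sentence says how it will be pursued: "The study will exam all the different systems to evaluate the histological necrosis after neo-adjuvant chemotherapy in all patients" operated on in the study period. So every system is to be looked at in the same patients.

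**Systems (Background).** Good and poor response "has been defined to different systems published in literature: true Percentage, Huvos System and Bologna System".

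**Design (Study Design).** "This is single institution cases series review of histological and clinical data".

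**Analysis (Statistics).** The section is one sentence: "To the case series will be applied a descriptive statistic".

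**Size (Material and Methods).** "We expect to find approximately 500 cases". As written, this is the yield of a database search for the histological diagnosis. It is not a calculated sample size, and it precedes the restriction to localized bone disease with neo-adjuvant chemotherapy and no radiotherapy before surgery.

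No section names an endpoint or criterion for judging the systems.

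**The concern.** Asking which of several tools is best calls for a yardstick and a comparison on that yardstick. The protocol supplies neither, and the one analytical statement that it makes points to description. An analyst could comply in full by tabulating how each system classifies the patients, and the only objective would remain unanswered. If a winner were still declared, it could be whichever system had the most favourable point estimate, with nothing to show whether the lead exceeds chance.

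The data are retrospective, so the outcomes already exist. A criterion that is left open can be settled after the results have been seen.

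The Background says that necrosis assessment "has allowed to identify patients who are candidates for more intensive or novel therapies". A published claim that one system is best may therefore influence how patients are classified as responders. That step is an inference: the protocol does not say that its result will change classification or treatment.

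**Working it through.** **1. Text check.** The plan gives no alpha, power, margin, effect size or event count, so there is no stated figure to reproduce.

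| Element needed to answer the aim | Where it could stand | What is there |
|---|---|---|
| Criterion for *best* | Objective, Background | None. The Objective says only best at determining histological response. The Background's phrase about the best predictive factor describes necrosis itself, not a system |
| Outcome data for that criterion | Material and Methods, Data Collection | Charts and records reviewed; no outcome named |
| Comparison between systems | Statistics | None; described as descriptive |
| Measure of uncertainty | Statistics | None named, though *descriptive* does not exclude one |

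The first row matters most, because it defines the objective. The last row alone could properly be left to a statistical analysis plan.

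**2. Precision of one system by itself (illustration).** Assumptions: all 500 cases analysable, no censoring before 5 years, and a share q of patients in one response group. The 5-year survival S of 50% or 70% is taken from the Background's historical rates, which are not design inputs.

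- Deaths D = 500 × (1 − S): 250 or 150.
- 95% half-width for survival in the group = 1.96 × √[S(1 − S)/(500q)]. For S = 0.5, q = 0.3: 1.96 × √(0.25/150) = 8.0 percentage points.
- SE(log hazard ratio) = 1/√[D q(1 − q)]. For D = 150, q = 0.3: 1/√31.5 = 0.178, so the 95% interval runs a factor exp(1.96 × 0.178) = 1.42 either way.

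| S | q | D | Half-width (points) | Hazard-ratio factor |
|---|---|---|---|---|
| 0.5 | 0.3 | 250 | 8.0 | 1.31 |
| 0.5 | 0.5 | 250 | 6.2 | 1.28 |
| 0.7 | 0.3 | 150 | 7.3 | 1.42 |
| 0.7 | 0.5 | 150 | 5.7 | 1.38 |

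These are unpaired, single-system figures. All systems are applied to the same patients, so a comparison must be paired, and its precision depends on how strongly the systems' errors are correlated.

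**3. How often the wrong system leads (simulation, all inputs assumed).** Criterion: concordance with time to event (Harrell, ties counted 0.5). Latent response is N(0,1); survival is exponential with log-hazard 0.6 per SD; 65% are event-free at 5 years, with censoring then; n = 500. Each system's score is the latent response plus a reading error of SD s, with error correlation r between systems. One system is left uncut; the others are cut into 3 and 4 groups (the protocol does not give the categories). The uncut system is truly ahead by 0.016 to 0.022 and 0.009 to 0.013.

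| s | Wrong leader, r = 0.5 | r = 0.8 |
|---|---|---|
| 0.3 | 7% | 3% |
| 0.6 | 22% | 12% |
| 1.0 | 36% | 26% |

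With r = 1 (one necrosis reading expressed in each system), the wrong leader appears in about 1% to 7% of runs over the same values of s.

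Two further results, again with r of 0.5 to 0.8 and n = 500, all systems now in three groups:

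- One system truly better by about 0.014 to 0.021 fails to lead in 9% to 27%.
- With a true advantage of 0.035, the right system leads in 96.3% to 98.5%, so a wide margin is visible without any formal method.

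**The case against.** **A statistical analysis plan may exist.** The form of the comparison and the type of interval are commonly left to one, and their absence from a protocol is no defect. This stands, and a reader should not infer that the missing interval method is itself the error. The undefined criterion is different: it fixes what the objective means. The label *descriptive* is also a statement in the protocol, and a later plan with a formal comparison would go beyond it.

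**Tension, not contradiction.** Study Design and Statistics agree with each other, and a descriptive analysis may set systems side by side, even with intervals. A reader might infer that the plan forbids a comparison. It does not; it simply requires none. Because description is a legitimate choice for a case series, rewording the aim is an acceptable remedy.

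**The criterion is implied.** The Background introduces the systems just after calling necrosis predictive, and two cited titles concern prognosis. Prognosis is thus the natural reading, but it remains an inference. Reader agreement might also be imagined as the yardstick. No section mentions a second reader, repeat scoring or reproducibility, so the documents give that reading no footing.

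**The error rates depend on separate readings.** This stands. The protocol does not say whether each system is read separately or derived from one reading, and under one shared reading the rates fall to a few percent. A reader might infer that the study will probably name the wrong system; the documents do not support that. Where the ordering is fragile, the true differences are also small, so a wrong choice costs little in discrimination.

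**Conclusion.** The point holds as a mismatch between aim and analysis. The only objective is to pick the best system, the stated analysis is descriptive, and nothing says what *best* means. Followed as written, the study either leaves its question unanswered or answers it by an informal ordering. Confidence in this is high, since it rests on the protocol's own text.

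Confidence in the size is low. The range of 3% to 36% for a wrong leader rests on separate readings with error correlation 0.5 to 0.8, assumed group numbers, an assumed prognostic effect and 500 analysable patients. The analysable number may be smaller: with 350, the 9% to 27% for one better system becomes 15% to 29%. With a shared reading, the chance of a wrong leader is only a few percent. The point does not depend on these figures. It should be fixed, because it concerns the sole conclusion that the study is meant to reach.

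**What to change.** Choose one of two routes.

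**Keep the comparative aim.** Amend Statistics to state:

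- the criterion for *best*, for example discrimination for event-free survival if prognosis is meant, with the event defined;
- that the paired difference between systems on that criterion will be reported, on the patients scored by all systems, with 95% confidence intervals (a bootstrap over patients would do);
- that *no system shown superior* is an admissible conclusion.

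Make sure that the CRF captures event and follow-up dates, and settle this before chart review. It would help to say whether each system is read separately or derived from one necrosis reading.

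Cost: two or three sentences and modest extra analysis. The main downside is that there may be no clear winner. In the separate-reading simulations with 500 patients, the paired 95% interval has a half-width of about 0.016 to 0.034 in concordance. A system truly better by about 0.014 to 0.021 is clear of both others in only 9% to 22% of runs, and one better by 0.035 in 41% to 54%. A shared reading would narrow the intervals. In the same simulations, a wrong system was clear of both others in at most 0.3%.

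**Or make the aim descriptive.** Reword the Objective to describe how each system classifies the patients, and drop *best*. Statistics can then stay as it is. Cost: one sentence, and the study gives up any ranking.

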**DATA COLLECTION**

Clinical data will be retrieved by patient charts.

A protocol-specific CRF reporting the results of the review will be provided.

A CRF is required and should be completed for each included subject.

**ETHICS AND QUALITY ASSURANCE**

The clinical trial protocol and its documents will be sent before initiating the study to the competent Authorities and Ethics Committees of each participating country for its approval.

The responsible investigator will ensure that this study is conducted in agreement with either the most updated Declaration of Helsinki and all the international and local laws that apply to clinical trials and to patient protection.

The protocol has been written, and the study will be conducted according to the principles of the ICH Harmonized Tripartite Guideline for Good Clinical Practice (ref: <http://www.emea.eu.int/pdfs/human/ich/013595en.pdf>).

## **INFORMED CONSENT**

For Scientific Institute for Research and Healthcare (IRCCS) informed consent form to the processing of personal data is not applicable as for the Article 110 bis, paragraph 4 of the New Privacy Code (GDPR) regarding the use of clinical activity data collected for research purposes

## **CONFIDENTIALITY**

In order to ensure confidentiality of clinical trial data as disposed the national and European applicable regulation, data will be only accessible for the trial Sponsor and its designees, for monitoring/auditing procedures, the Investigator and collaborators, the Ethics Committee of each corresponding site and the Health Authority.

Investigator and the Institution will allow access to data and source documentation for monitoring, auditing, Ethic Committee revision and inspections of Health Authority, but maintaining at all times subject personal data confidentiality as specified in the “Directive 95/46/EC of the European Parliament and of the Council of 24 October 1995”.

The Investigator must guarantee that patient anonymity is kept at all times and their identity must be protected from unauthorized persons and institutions.

All patients included in the study will be identified with a numeric code, so that no identifiable personal data will be collected (pseudo anonymization)

The Investigator must have and conserve a patients' inclusion registry where it figures the personal data of the patient: name, surname, address and corresponding identification code into the study, this register will be kept on the Investigator File.

## **PUBLICATION OF RESULTS**

The results from this study will be published or shown at scientific conferences.

The final publication of the study results will be written by the Principal Investigator.

## SPONSOR ROLE AND RESPONSIBILITY

The sponsor is the sole owner of the data and is responsible of all the clinical trial activities from study design, development, data collection, management, analysis, interpretation of data, writing and the decision to submit the report for publication written by the Principal Investigator,

